6.4. Sample Size

Up to 30 patients will be entered in each cohort, monitored after every 6 patients according to the interim analyses plans below. The selection of 30 patients per cohort combines feasibility of accrual and operating characteristics of the decision rules. If a cohort accrues to full size and has a 50% SNS success rate (15/30) then the 90% credible interval using a prior of beta(1,1) would be (35.7%, 64.3%). Patients who complete baseline measures and sign consent but who are not able to undergo SNS implant for insurance issues will not be evaluable for this study. Accrual numbers have been inflated by 10% to allow for unevaluable patients taken off study for a total study enrollment of up to 66 patients to have an evaluable 60 patients.

6.5. Interim Analyses

A Bayesian sequential monitoring design (Thall et al. 1995 and 1998)[27, 28] will be used to monitor the trial for response and adverse events. Interim assessments will be performed in groups of 6 patients, with accrual held for evaluation for each cohort until enough information is available to determine the outcome. Each patient cohort will be evaluated separately and will continue if patients are exhibiting reasonable adverse event rates and SNS response rates. If one cohort stops, the other cohort will continue according to the monitoring rules. Calculations were performed in MultcLean Desktop version 2.1.0.

Interim Analyses for Futility

A patient will be considered to have SNS success as defined above. The patient cohort will be stopped early if $\Pr[\theta_S < 0.50 | \text{data}] > 0.95$, where θ_S denotes the SNS success rate. That is, given the outcomes from the patients who have already been evaluated, if it is determined that there is a more than 95% chance that the response rate is less than 50% (constant), the arm will be stopped for futility. Assuming a prior distribution of θ_S for each experimental treatment of $\sim \text{beta}(1,1)$, pre-defined stopping boundaries corresponding to this probability criterion are provided in the following table.

If there are this many patients evaluable for SNS success	6	12	18	24	30*
Stop the cohort if there are this many or fewer SNS successes	0	3	5	7	10

* The cohort will stop at 30 regardless of the number of SNS successes, but if there are 10 or fewer, then the implant is not promising enough for future trials in this patient cohort.

Assuming the cohort does not stop for adverse events first, 6 patients will be accrued. If none of the 6 patients have SNS success, stop the cohort and the implant will be declared as ineffective for this population. Patients will continue to be enrolled on the other cohort as long as it is open. If there is at least 1 success, the next 6 patients will be entered in the cohort, unless they need to stop according to the adverse event boundaries below. Continue checking after every 6 patients for sufficient SNS success assuming the trial does not stop for adverse events first. The operating characteristics for efficacy and adverse events are summarized after the adverse event rules below.

Interim Analyses for Safety

Under the same model described for SNS success, adverse events will be monitored assuming an *a priori* probability of limiting adverse events following Beta(0.6, 1.4) in the current patient cohort. Cohort limiting events (CLE) are defined as perioperative cardiovascular events, readmission if it is related to the SNS procedure, SNS lead removal due to any reason other than failure, or perioperative death due to surgery or complications. The patient cohort will be terminated if $\text{Prob}(\text{CLE} > 0.30 | \text{data}) > 0.95$. The specific rules for stopping after each cohort are included in the table here.

If there are this many patients (or more) with CLE	5	7	9	12	14
Stop the patient cohort if there are this many (or fewer) patients who are evaluable (have CLE, had battery implant without CLE, or had leads removed for failure without CLE.)	6	12	18	24	30*

* The cohort will stop at 30 patients, but if 14 or more patients have CLE, then the implant is too dangerous for this cohort.

Six patients will be accrued before the first analysis. If 5 or more of the 6 patients have CLE, stop the cohort and the implant will be declared as too dangerous for this population. If there are 4 or fewer CLEs, enroll the next 6 patients assuming the cohort didn't stop for futility.

The operating characteristics are summarized in the following table:

The operating characteristics for each patient cohort are shown in the following table.

		Stop if $\text{Prob}\{\theta_S < 0.50 \text{data}\} > 0.95$ or Stop if $\text{Prob}\{\text{CLE} > 0.30 \text{data}\} > 0.95$	
True	True	Pr(stop early)	Mean Number of Median

Adverse Event Rate	Response Rate		Patients	(25 th %ile, 75 th %ile)
0.1	0.30	0.68	18.5	12 (12, 30)
0.2	0.30	0.68	18.5	12 (12, 30)
0.3	0.30	0.71	18.0	12 (12, 30)
0.4	0.30	0.79	16.5	12 (12, 24)
0.5	0.30	0.90	14.0	12 (12, 18)
0.1	0.40	0.33	24.6	30 (18, 30)
0.2	0.40	0.33	24.5	30 (18, 30)
0.3	0.40	0.38	23.7	30 (12, 30)
0.4	0.40	0.55	21.0	18 (12, 30)
0.5	0.40	0.79	16.8	12 (12, 24)
0.1	0.50	0.10	28.3	30 (30, 30)
0.2	0.50	0.11	28.1	30 (30, 30)
0.3	0.50	0.18	27.1	30 (30, 30)
0.4	0.50	0.40	23.7	30 (18, 30)
0.5	0.50	0.72	18.4	18 (12, 30)
0.1	0.60	0.02	29.6	30 (30, 30)
0.2	0.60	0.03	29.5	30 (30, 30)
0.3	0.60	0.10	28.4	30 (30, 30)
0.4	0.60	0.34	24.7	30 (18, 30)
0.5	0.60	0.69	19.0	18 (12, 30)
0.1	0.70	0.003	30.0	30 (30, 30)
0.2	0.70	0.01	29.8	30 (30, 30)
0.3	0.70	0.08	28.7	30 (30, 30)
0.4	0.70	0.33	25.0	30 (18, 30)
0.5	0.70	0.68	19.1	18 (12, 30)

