6.3. Endpoints

Primary Endpoints

The primary endpoint is SNS Success. *SNS Success* will be measured as a patient having the battery implanted at visit 3 which can only happen if they've achieved improvement in fecal incontinence at visit 3. Patients who do not have the SNS placed, for any reason other than insurance coverage issues, will count as not having a success.

Fecal incontinence will be measured by the physician as the total number of gas, mucus, liquid stool, and solid stool accidental leakage events reported in the bowel diaries.

Improvement will be determined by the physician based on bowel diary comparisons recorded before SNS lead placement at visit 1 to after lead placement at visit 2. This is done at visit 3 when the patient presents for consideration of placement of the implantable battery. Any patient who comes in for SNS placement but the SNS cannot be successfully placed for any reason other than insurance reasons will count as not having improvement. Patients meeting this improvement will have their *battery implanted*. Patients will be counted as having their battery implanted if it is implanted at Visit 3 if they had the SNS placed at Visit 2.

Secondary Endpoints

- **FISI** overall questionnaire summary
- **FIQOL** overall questionnaire summary
- **ARM** score
- **EQ-5D-5L**
- **ICSmaleSF** or **ICIS-FLUTS** (females)
- **MSKCC BFQ (for restorative surgery cohort)**
- **LARS Score Bowel Function Questionnaire (for restorative surgery cohort)**

- **CCIS (for radiation only cohort)**
- **Bowel Diaries**
- **Bladder Diaries**
- **EORTC QLQ-CR29**
- **FISI, FIQOL, EQ-5D-5L, ICSmaleSF or ICIS-FLUTS, MSKCC, EORTC QLQ-CR29 and CCIS will also be collected at 1 and 3 years for long-term evaluation.**

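### The safety stopping table reuses full-group CLE counts for smaller evaluable numbers, where at many counts it fails to trigger a stop that the plan's own 0.95 criterion requires

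*Combined protocol and SAP*

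**What the plan says.** Section 6.5, under Interim Analyses for Safety, gives the CLE rate a Beta(0.6, 1.4) prior and terminates a cohort if Prob(CLE > 0.30 | data) > 0.95. It then offers a table as the specific form of this rule. One row, "If there are this many patients (or more) with CLE", holds 5, 7, 9, 12 and 14. The other, "Stop the patient cohort if there are this many (or fewer) patients who are evaluable", holds 6, 12, 18, 24 and 30. Evaluable for safety means one of three things: "have CLE, had battery implant without CLE, or had leads removed for failure without CLE".

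On timing, "Interim assessments will be performed in groups of 6 patients", with accrual held until outcomes can be determined, and "Six patients will be accrued before the first analysis". The text after the table stops the cohort at 5 or more CLEs among the 6, and enrols the next group if there are 4 or fewer. That second sentence gives no denominator.

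The success endpoint uses a wider set. Section 6.3 states: "Patients who do not have the SNS placed, for any reason other than insurance coverage issues, will count as not having a success". Section 6.2 counts as evaluable anyone who consents, completes the visit 1 questionnaires and is not denied by insurance, but restricts the endpoint analyses to patients who return for the placement appointment.

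**The concern.** A patient in whom no lead is placed, and who has no CLE, fits none of the three safety categories but can count as a non-success. Section 6.3 expressly keeps patients who attend for placement and in whom it fails. Section 5 adds another route: patients taken off study before placement for laboratory values or infection. A group of six evaluable for success can therefore hold fewer than six evaluable for safety, and the words in parentheses in the table appear to anticipate this.

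A fixed number of CLEs is stronger evidence of harm in fewer patients, so a boundary set for 6 can be too high for 4 or 5. The plan would then hold two safety rules that disagree, without saying which one governs. This is its only formal safety stopping rule, and section 7 relies on it.

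**Working it through.** **Inputs (section 6.5).** Prior Beta(0.6, 1.4); criterion Prob(CLE > 0.30 | data) > 0.95; table counts 5/7/9/12/14 at 6/12/18/24/30.

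**Formula.** With x CLEs in n safety-evaluable patients the posterior is Beta(0.6 + x, 1.4 + n − x). The boundary at n is the smallest x whose posterior probability above 0.30 exceeds 0.95.

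**Step 1: reproduce the table at full groups.**

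| n | Table count | Posterior at that count | Posterior at one CLE fewer |
|---|---|---|---|
| 6 | 5 | 0.991 | 0.945 |
| 12 | 7 | 0.969 | 0.905 |
| 18 | 9 | 0.951 | 0.883 |
| 24 | 12 | 0.974 | 0.938 |
| 30 | 14 | 0.967 | 0.929 |

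All five counts are right. Exact recursion over looks at 6, 12, 18 and 24, with CLE and success independent, also reproduces the operating characteristics. Adverse event rate 0.3 with response rate 0.5 gives 0.176 and mean N 27.1 (plan: 0.18 and 27.1). Rates 0.5 and 0.7 give 0.684 and 19.1 (plan: 0.68 and 19.1). The published figures therefore describe full groups of six.

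**Step 2: apply the criterion at smaller n.** The table count is that of the first column at or above n.

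| Evaluable n | Criterion boundary | Table count |
|---|---|---|
| 3 | 3 | 5 |
| 4–5 | 4 | 5 |
| 6 | 5 | 5 |
| 7–8 | 5 | 7 |
| 9–10 | 6 | 7 |
| 11–12 | 7 | 7 |
| 13–15 | 8 | 9 |
| 16–18 | 9 | 9 |
| 19–20 | 10 | 12 |
| 21–23 | 11 | 12 |
| 24 | 12 | 12 |
| 25 | 12 | 14 |
| 26–28 | 13 | 14 |
| 29–30 | 14 | 14 |

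Posterior probabilities where the criterion is met and the table gives no stop: 4/4 0.992, 4/5 0.975, 5/8 0.954, 6/10 0.962, 8/15 0.960, 10/20 0.961, 11/23 0.955. The table count is never below the criterion boundary in this range, so the parenthesis causes no wrong stop.

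**Step 3: size.** The documents give no rate of non-placement, so the shortfalls below are assumptions. The figures are the probability of an early stop over looks 1–4 under the safety rule alone, by exact binomial recursion, table against criterion.

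| Safety-evaluable at looks 1–4 | True CLE 0.30 | True CLE 0.40 | True CLE 0.50 |
|---|---|---|---|
| 6/12/18/24 (full) | 0.08 v 0.08 | 0.33 v 0.33 | 0.68 v 0.68 |
| 5/11/17/23 (one missing overall) | 0.05 v 0.09 | 0.25 v 0.35 | 0.60 v 0.70 |
| 5/10/15/20 (one missing per six) | 0.02 v 0.10 | 0.12 v 0.34 | 0.37 v 0.66 |

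With a shortfall, the criterion keeps stopping probabilities close to the full-group values. The table lets them fall.

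**The case against.** Several points count against making more of this.

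- **The table is not miscalculated.** Every stop it lists is valid, and it reproduces at the planned looks. A reader might infer that it is right only at 6, 12, 18, 24 and 30, or fails whenever one patient lacks a lead. Neither holds: it equals the criterion at 11, 16, 17 and 29. With one patient missing at a look (5, 11, 17, 23 or 29 evaluable), the two differ only at 5 and 23.
- **The table does not order continuation at every such count.** The only explicit instruction to continue is at the first look, and it follows a sentence about 6 patients, so 6 may be its intended denominator. At later looks the plan simply gives no stop. The criterion is itself stated without conditions and could be taken to govern.
- **Holding accrual could cure the problem** if it meant waiting for exactly 6, 12, 18 or 24 safety-evaluable patients. The text does not say so, and the parenthesis would then be needless. A patient with no lead and no CLE will not become safety-evaluable by waiting.
- **The shortfall may be small.** Enrolment requires insurance pre-authorisation, and a failed placement with a CLE is still safety-evaluable. Section 6.2 is narrower than 6.3 for patients who never return for placement. Failed placements remain in the success set under both sections.
- **Step 3 covers safety only.** Patients without a lead count as non-successes, which makes a futility stop more likely. Joint stopping under a shortfall was not computed.

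These points limit the scope and size of the concern. They leave two rules that disagree at counts the table's own wording covers.

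**Conclusion.** The concern holds in limited form. At many evaluable counts covered by the parenthesis, the table does not trigger a stop that the stated criterion requires, and the plan does not say which governs. At the first look, 4 CLEs in 4 or 5 evaluable patients meets the criterion, while the accompanying sentence read literally enrols the next six. The discrepancy is one-sided, toward continuing.

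Its size is conditional. At a true CLE rate of 0.40 the loss in early stopping probability is nil with full groups, about 0.10 (0.35 − 0.25) with one patient missing overall and about 0.22 (0.34 − 0.12) with one missing per six. At 0.50 the losses are nil, 0.10 (0.70 − 0.60) and 0.29 (0.66 − 0.37). The heaviest case should not be read as an expectation, since nothing in the documents supports a particular rate. Nor are the published operating characteristics wrong; they simply do not describe looks with a shortfall.

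**What to change.** Either of two changes reconciles the table, the first-look sentence and the criterion.

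1. State that the 0.95 criterion governs at the actual number of safety-evaluable patients. Replace the five columns with the boundary for each n from 3 to 30 (for example 4 at 5, 6 at 10, 8 at 15, 10 at 20, 11 at 23), and give the first-look continue sentence a matching denominator.
2. Time the safety looks at exactly 6, 12, 18 and 24 safety-evaluable patients and delete the parenthesis.

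The first costs a longer table. The second may delay a look while replacements for non-evaluable patients are accrued. Neither changes the prior, the threshold or the sample size.

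### A patient whose lead placement was started but failed enters the safety denominator only if a cohort-limiting event occurs, so the monitored rate per attempted patient is biased upward (minor)

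*Combined protocol and SAP*

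**What the plan says.** Section 6.5 (Interim Analyses for Safety) monitors CLEs in each cohort. They include "perioperative cardiovascular events, readmission if it is related to the SNS procedure, SNS lead removal due to any reason other than failure", and also perioperative death. A cohort stops when the posterior probability that the CLE rate exceeds 0.30 is above 0.95. The tabulated boundaries are 5, 7, 9, 12 and 14 CLEs at 6, 12, 18, 24 and 30 evaluable patients, where evaluable patients are those who "have CLE, had battery implant without CLE, or had leads removed for failure without CLE".

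Section 6.3 deals with failed placement on the efficacy side: "Any patient who comes in for SNS placement but the SNS cannot be successfully placed for any reason other than insurance reasons" counts as not improved. Section 6.2 includes everyone who returns for the placement appointment in the endpoint analyses.

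The timing of the looks is described in two ways. The text of Section 6.5 speaks of accrued patients ("Interim assessments will be performed in groups of 6 patients"). The safety table counts "this many (or fewer) patients who are evaluable".

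**The concern.** A patient whose stage 1 procedure was started but whose lead could not be placed has no battery and no lead in place to be removed later. Of the three routes into the safety denominator, only a CLE is open to that patient. A perioperative cardiovascular event, a related readmission and a perioperative death all need no placed lead, so this can happen. With an event, the patient is in numerator and denominator. Without one, the patient is in neither. Entry to the denominator thus depends on the outcome being monitored, and the proportion compared with 0.30 is not the rate per attempted patient.

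The printed operating characteristics treat every patient as counted for both CLE and success, so the definition of evaluable does not match the calculation behind them. At stake is a cohort closed, and the implant declared too dangerous, on a rate that leaves out some patients who went through the procedure without harm.

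**Working it through.** **Inputs from Section 6.5.** Prior: "probability of limiting adverse events following Beta(0.6, 1.4) in the current patient cohort". Threshold 0.30, cutoff 0.95, looks at 6, 12, 18, 24 and 30. The futility rule has a Beta(1,1) prior and boundaries 0/3/5/7/10.

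**Assumptions not in the documents.** f = share of CLE-free patients with a failed placement: 5, 10 or 20%. CLE risk is the same whether or not the lead is placed.

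**1. Reproduce the plan.** The boundary at n is the smallest x for which 1 − BetaCDF(0.30; 0.6 + x, 1.4 + n − x) > 0.95. This gives 5/7/9/12/14, as printed. For example, 4/6 gives 0.945, 5/6 gives 0.991 and 7/12 gives 0.969. An exact calculation with CLE and response independent, and each patient counted in both denominators, reproduces all 25 early-stopping probabilities within 0.01. At CLE 0.30 and response 0.60 it gives 0.101 and a mean of 28.4 patients, against the printed 0.10 and 28.4.

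**2. Monitored rate.** With true rate c, monitored rate = c / [c + (1 − c)(1 − f)]. For c = 0.30:
- f = 5%: 0.30 / (0.30 + 0.70 × 0.95) = 0.30 / 0.965 = 31.1%
- f = 10%: 0.30 / (0.30 + 0.70 × 0.90) = 0.30 / 0.93 = 32.3%
- f = 20%: 0.30 / (0.30 + 0.70 × 0.80) = 0.30 / 0.86 = 34.9%

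**3. Early safety stopping.** Safety rule alone, looks at 6, 12, 18 and 24, exact enumeration, c = 0.30. With all attempts counted it is 0.083 at every f. With the current definition:

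| Reading of the rule | f = 5% | f = 10% | f = 20% |
|---|---|---|---|
| Look at each sixth evaluable patient | 0.100 | 0.121 | 0.179 |
| Look at each sixth accrued patient, posterior on the actual evaluable number | 0.099 | 0.116 | 0.162 |
| Look at each sixth accrued patient, table with its or-fewer wording | 0.083 | 0.083 | 0.094 |

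At c = 0.10, early stopping is below 0.001 under every reading for f up to 20%.

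**4. One patient at the first look.** Four CLEs in 6 attempted patients gives 0.945, so the cohort continues. If one of the six is a failed placement without CLE and is dropped, 4/5 gives 0.975, which meets the stated criterion. The table read literally still needs 5 CLEs at 6 or fewer evaluable patients, so it would continue. The readings in step 3 diverge in the same way.

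**5. Sensitivity to the second assumption.** Suppose unplaced patients never have a CLE, the rate in placed patients is 0.30, and 5, 10 or 20% of all attempts fail. The monitored rate is then 0.300, while the rate per attempted patient is 0.30 × 0.95 = 0.285, 0.30 × 0.90 = 0.270 or 0.30 × 0.80 = 0.240. The monitored rate is then right for placed patients and too high only for attempted patients.

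**The case against.** The strongest reply is that stopping may barely change. Section 6.5 describes the first look by accrual ("If 5 or more of the 6 patients have CLE, stop the cohort"). With the or-fewer table, the boundary is in effect a CLE count, and dropping a CLE-free patient rarely moves it. This stands for that reading: there is no visible change at 5 or 10%. It does not settle the matter, because the table counts evaluable patients and the governing criterion is a posterior, which moves with the denominator.

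Other points that stand:
- No failed-placement rate is given, and nothing in the documents supports 10 or 20% in particular.
- A true rate of 0.30 is the threshold itself. Section 7 calls the trial low risk.
- A case cancelled before stage 1 starts also fits the Section 6.3 wording but has no procedural exposure, so it need not be in a safety denominator.
- *Failure* is not defined in the safety table. A lead tried and withdrawn in the operating room could be read as removed for failure, which would close part of the gap. Section 5 uses removal for a stimulator that did not work or for too small a symptom decrease, which favours the non-response reading.

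A reader might infer more than the documents support:
- **That the chance of false stopping doubles.** The rise from 0.083 to 0.179 needs one look timing and a 20% failed-placement share.
- **That cohort 2 is hit hardest because placement is harder in an irradiated pelvis.** No passage says so.
- **That the published CLE rate will be biased.** Section 6.6 reports CLEs descriptively and does not tie them to this denominator.

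**Conclusion.** The point holds as a minor one. The safety denominator as worded depends on the outcome, and no other section repairs it. The monitored rate overstates the rate per attempted patient whenever some placements fail without a CLE and CLEs also occur. At a true rate of 30% the overstatement is 1.1, 2.3 or 4.9 percentage points for assumed failed-placement shares of 5, 10 or 20%. The effect on early stopping ranges from none to about 0.10 (0.179 − 0.083 = 0.096), depending on that share and on a look rule the plan leaves open. The tabulated boundaries are correct for their stated prior and criterion. The direction is toward closing a cohort too readily, so a reader should not take this as a rule that conceals harm.

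**What to change.** In the safety table of Section 6.5:
- Define the denominator as every patient in whom the stage 1 procedure was started, whatever the placement result.
- Count a failed placement without CLE as CLE-free.
- State that *failure*, in leads removed for failure, means non-response.
- Use the same set when CLEs are tabulated under Section 6.6.

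The cost is one row of wording and one definition, with no new data. The boundaries 5/7/9/12/14 depend only on the prior, the threshold and the count, so they stay. The printed operating characteristics also stay, since they already assume that every patient is counted.

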Visit 2 (Sacral Nerve Stimulator Lead Placement): Surgery for stage 1 sacral nerve stimulator placement will occur within 30 days after enrollment in the study. The patient will arrive at the pre-operative holding areas at UTMDACC's main campus for their outpatient surgery. The representative for the implantable SNS company (Medtronic) will be present at the operation for assistance with placement of the leads per standard of care and for assistance with patient education following lead placement. The patients are sent home with a diary to record daily bowel and bladder habits during the interval period.

Visit 3 (Assessment of Symptoms and Battery Implantation or Lead Removal): Surgery for stage 2 sacral nerve stimulator battery implantation or lead removal will occur around 2 weeks (+7 days) after SNS placement. The patient will arrive to the holding area with their post-implantation bowel and bladder habit diary from visit 2. Review of the bowel diary information and a review of symptoms from visit 1 and visit 2 with the patient will be completed and then a decision made to either implant the battery or remove the stimulator leads as per standard of care. If the bowel diary reveals $\geq 50\%$ decrease in FI or LARS symptoms between visit 1 and visit 2, the external temporary battery will be replaced with an implantable battery. If the bowel diary reveals $< 50\%$ decrease in FI or LARS symptoms, the previously placed leads and external battery will be evaluated for proper positioning and functioning in the OR and removed if they remain properly positioned. Following the procedure, the patient is discharged home. If the device is removed, their participation in the study is complete, but data collected to this point will still be used in study analysis and reporting.

Visit 4 (Post-operative Assessment): Post-operative evaluation. The patients return to clinic at 1 month (+/- 2 weeks) after completion of visit 3 for a wound evaluation, device check, and symptom review. At this point, the patients will complete study questionnaires (on paper, over the phone/teleconference system, or electronically through REDCap) and undergo a repeat ARM.

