Visits 5 (1-Year Follow Up) and 6 (3-Year Follow Up): Patients will return to clinic at 1 and 3 years (+/- 3 months) for evaluation, per routine standard of care, from their SNS battery for evaluation. Patients will again complete validated questionnaires (on paper, over the phone/teleconference system, or electronically through REDCap) at this visit. After collection of this data, their participation in this study is complete. If for any reason patients are not able to return to the clinic at these time points, study questionnaires may be filled out via mail or over the phone/teleconference system, or electronically through REDCap.

Table 1. Study Assessment Calendar

	Initial Evaluation/ Visit 1	Visit 2 (+ 4 weeks)	Visit 3 (+ 7 days)	Visit 4 (+/- 2 weeks)	Assessment at 1 and 3 years*
--	--------------------------------	------------------------	-----------------------	--------------------------	------------------------------

Physical exam + anorectal manometry + Post-void residual Bladder scan	X			X	
SNS Lead Placement		X			
Battery Implantation or Lead Removal			X		
FIQoL and FISI Instrument	X			X	X
MSKCC Bowel Function Instrument	X			X	X
LARS Score Questionnaire	X			X	X
EORTC QLQ-CR29	X			X	X
Cleveland Clinic Incontinence Score Instrument	X			X	X
EQ-5D-5L Instrument	X			X	X
ICSmaleSF or ICIS- FLUTS (as appropriate) Instrument	X			X	X
Bowel/Bladder Diary	X	X			
Adverse Events**			X		

* +/- 3 months

** See Section 7. Risk Management

Clinical Data Collection

Data regarding patients, tumors, treatments, and disease/vital status will be obtained from existing medical records. Patient data collected will include, but is not limited to: demographic information, lab values, comorbidities and medical history, medications, test results (i.e., EKG). Tumor data collected will include, but is not limited to: site, stage, histology, distance from anal verge, histologic grade, clinical TNM stage, method of clinical stage, tumor size, biomarker status (e.g., microsatellite status, KRAS, BRAF mutation status, etc.) as available. Treatment data for the primary cancer diagnosis will be collected including chemotherapy and radiation regimens as well as surgical procedures, complications and outcomes. Clinical data will be collected until the patient is taken off study.

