7. RISK MANAGEMENT

Restore is a low risk trial. Any of the risks encountered by the participant are those associated with surgery for the treatment of fecal incontinence or LARS. In the event that readmissions or SNS lead removals are high, the study will be terminated as described in the previous section. We feel that any risk associated with participation in *Restore* is minimal and will be offset by improved patient reported outcomes. The knowledge obtained by the study personnel regarding the feasibility of sacral nerve stimulation for the treatment of fecal incontinence and LARS in association with colorectal cancer will be used to assess the potential of expanded cohorts as previously described. Adverse events (AE), \geq grade 3, using CTCAE v. 4 and serious adverse events (SAE) related to the procedure that occur within 30 days after will be reported. Reportable AE and SAE would include, but are not limited to, lead migration, wound infection, pneumonia, intractable pain related to surgical complications such as wound infection, unplanned or unanticipated readmission within 30 days, stroke, myocardial infarction, perioperative cardiovascular events, readmission if it is related to the SNS procedure, SNS lead removal due to any reason other than failure, or perioperative death due to surgery or complications.

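### Section 6.5 sets no follow-up window after stage 2 before a patient counts as free of a cohort-limiting event, so late events can be missing at a safety look

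*Combined protocol and SAP*

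**What the plan says.** - **The rule (Section 6.5, Interim Analyses for Safety).** CLEs are perioperative cardiovascular events, SNS-related readmission, lead removal for any reason except failure, and perioperative death. No time window is attached. A patient is evaluable after a CLE, or when the patient "had battery implant without CLE, or had leads removed for failure without CLE".
- **The looks (Section 6.5).** Each cohort is assessed after every 6 patients, up to 30. Accrual is held until there is enough information to determine the outcome; no duration is given.
- **Timing (Section 5, Study Visits).** Stage 2 follows lead placement by about 2 weeks (+7 days). For implanted patients, "The patients return to clinic at 1 month (+/- 2 weeks) after completion of visit 3". For the others, "If the device is removed, their participation in the study is complete", although data collected up to then are still used.
- **Assessment calendar (Table 1).** As the text was extracted, the "Adverse Events" row has one mark, in the Visit 3 column, and a footnote pointing to Section 7.
- **Reporting (Section 7).** Grade 3 or higher adverse events, and serious adverse events related to the procedure, "that occur within 30 days after will be reported". The list of reportable events repeats all four CLE components. The section does not say which of the two operations starts the 30 days.
- **Final analysis (Section 6.6).** Safety is analysed once all patients have completed four visits or are off study.

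**The concern.** Some listed CLEs cannot be seen on the day of stage 2. A patient who has just received a battery goes home with the lead in place, so removal of that lead comes later. Stage 2 is an outpatient operation, so a readmission caused by it also comes later. If a team applies the evaluability wording literally, the last patients before a look can enter the denominator as CLE-free before these events could have happened. The error goes one way, towards too few stops.

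This matters most in the radiation-only cohort. Section 6.1 describes it as a preliminary trial to establish safety, and Section 2 says there are no published data on SNS in such patients. Section 7 relies on the Section 6.5 rule if readmissions or lead removals are high, and the plan has no other numerical safety stopping rule.

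**Working it through.** **Step 1: set the passages side by side.** If the 30 days in Section 7 run from lead placement, they end 30 - 14 = 16 days after a stage 2 done at 2 weeks, and 30 - 21 = 9 days after one done at 3 weeks. If they run from stage 2, a Visit 4 at the early edge of its window (about 2 weeks) falls before they close. On either reading, an explanted patient has no scheduled contact after stage 2.

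**Step 2: reproduce the boundaries.** The inputs are the prior ("limiting adverse events following Beta(0.6, 1.4) in the current patient cohort") and the criterion: "The patient cohort will be terminated if" Pr(CLE rate > 0.30 | data) > 0.95. The boundary at n patients is the smallest x with Pr(Beta(0.6 + x, 1.4 + n - x) > 0.30) > 0.95.

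| n | x - 1: probability | x: probability | Plan |
|---|---|---|---|
| 6 | 4: 0.945 | 5: 0.991 | 5 |
| 12 | 6: 0.905 | 7: 0.969 | 7 |
| 18 | 8: 0.883 | 9: 0.951 | 9 |
| 24 | 11: 0.938 | 12: 0.974 | 12 |
| 30 | 13: 0.929 | 14: 0.967 | 14 |

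All five agree, including the worked first look: "If 5 or more of the 6 patients have CLE, stop the cohort". The futility boundaries 0, 3, 5, 7 and 10 also reproduce.

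**Step 3: reproduce the operating characteristics.** An exact recursion in groups of 6 was used, with CLE and response independent, and early stopping meaning a stop at 6, 12, 18 or 24 patients. All 25 printed probabilities reproduce within 0.01. At response 0.70 and CLE rates 0.3, 0.4 and 0.5, the recursion gives 0.085, 0.331 and 0.684; the plan prints 0.08, 0.33 and 0.68. The recursion takes every patient's CLE status as fully known at each look, so the printed figures hold under that condition.

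**Step 4: let some CLEs be unknown at the look.** Let f be the share of CLE patients known at the look. The documents give no value; f from 0.50 to 1 is an assumption. Two cases were run at response 0.70.

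- *Never recovered:* the observed rate is f times the true rate. For example, 0.75 × 0.40 = 0.30 and 0.50 × 0.40 = 0.20, whose probabilities (0.08 and 0.01) can be read from the plan's own table.
- *Updated:* only the newest group of 6 is known with share f; earlier groups are complete by the next look.

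Pr(stop early) at true CLE rates 0.40 / 0.50:

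| f | Never recovered | Updated |
|---|---|---|
| 1 | 0.33 / 0.68 | 0.33 / 0.68 |
| 0.90 | 0.21 / 0.51 | 0.29 / 0.64 |
| 0.75 | 0.08 / 0.25 | 0.24 / 0.57 |
| 0.50 | 0.01 / 0.03 | 0.15 / 0.43 |

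If only the last patient before each look is incomplete, f = 0.50 gives 0.29 / 0.64 (CLE rule alone; futility adds almost nothing at response 0.70).

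**The case against.** A reader might infer that the rule closes CLE status at Visit 3 and so undercounts events by design. The documents do not say that. Section 6.5 names no visit or day, and each non-event category carries the condition that no CLE has occurred. The accrual hold can be read as waiting for late events, and nothing excludes them from later looks.

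A reader might also take Table 1 to mean that adverse events are collected only at Visit 3. Its footnote points to the 30-day window in Section 7, and the extracted layout cannot rule out a cell that spans several visits.

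Three further points stand. Implanted patients have Visit 4 and stay in follow-up to 3 years, so their late events can be picked up. Stage 1 complications have about 2 weeks to appear before stage 2. The never-recovered column is a worst case: it treats the first 6 patients as still incomplete at the 24-patient look.

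These points limit the size but do not close the gap. The hold has no duration, and the only stated test of safety evaluability can be met on the day of stage 2. Section 7 does not govern Section 6.5. For explanted patients, the end of participation and the 30-day reporting promise conflict, and no scheduled contact would collect the events.

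**Conclusion.** The point holds as an undefined window. Followed as written, the rule can miss stage 2 events at a look, and events in explanted patients may never be collected. The effect is a lower chance of a safety stop.

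The size cannot be fixed from the documents. It rests on the assumed share known at the look, on whether later looks are updated, and on CLE and response being independent. With 75% known and a true CLE rate of 0.50, early stopping falls from 0.68 to 0.57 with updating, or to 0.25 without recovery. With 90% known and updating, the loss is small (0.68 to 0.64).

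It would be wrong to conclude that the boundaries or operating characteristics are in error; they reproduce. This is a cheap improvement to the safety rule.

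**What to change.** 1. In Section 6.5, count a patient as CLE-evaluable when a CLE has occurred, or when the 30-day window of Section 7 has passed since the last study procedure (battery implant or lead removal). Use only such patients at each look, and state that events learned later update later looks.
2. In Section 7, say that the 30 days run from each procedure and that the same window governs Section 6.5.
3. Reconcile the Visit 3 text in Section 5 with Section 7 by keeping explanted patients on study for one remote contact at 30 days.
4. In Table 1, mark adverse events at Visits 2, 3 and 4, and add that contact.

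Boundaries, sample size and printed operating characteristics do not change. The cost is protocol wording, one remote contact per explanted patient, and about 30 days' wait at each look. With four looks before the cohort is full, that is at most about 4 × 30 = 120 days per cohort, and less if the accrual hold would already have covered part of it.
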